**I. Research Title: Survey on the Reproductive and Child-Rearing Situations of Patients with Severe Mental Disorders**

**II. Summary of the Research Plan**

**1. Background**

The intergenerational impact of severe mental illness constitutes a critical public health challenge. In Australia, 23.3% of children have at least one parent with mental illness [1], while China's national registry currently documents over 6 million cases of severe mental disorders, with 60% of affected individuals being married or previously married. This suggests a substantial population of children raised by parents with mental illness nationwide.

Existing evidence demonstrates that parental mental disorders exert multidimensional burdens across social, familial, and psychological domains [2]. Developmental outcomes for these children show increased vulnerability to both physical and mental health complications compared to peers [2]. Adolescence represents a particularly critical period, as emerging psychosocial engagement coincides with heightened risk for psychological distress [3]. Comparative studies indicate these children exhibit poorer coping strategies, lower self-esteem, and greater internalizing/externalizing behaviors than controls [4], underscoring their need for targeted support systems.

The transition to adulthood presents additional challenges, as this developmental stage coincides with typical onset periods for mental disorders. Longitudinal data reveal alarmingly high heritability risks (41-77%) among offspring of affected parents [2]. Adult children of depressed parents demonstrate elevated rates of depressive symptomatology, somatic complaints, stress reactivity [5], and functional impairment [6,7].

Despite these documented risks, China lacks systematic data regarding family formation

patterns and child-rearing circumstances among mentally ill populations. This epidemiological survey will establish foundational data to inform national mental health service planning and policy development.

## **2. Research Objectives**

This multicenter study aims to:

Characterize reproductive histories, child-rearing practices, and socioeconomic conditions among patients with severe mental disorders;

Identify demographic and clinical correlates of family formation patterns;

Provide empirical evidence to guide mental health service policy formulation.

## **3. Methodology**

### **3.1 Study Design:**

Multicenter cross-sectional survey

### **3.2 Study Population:**

Registered patients (N=100,000-200,000) aged 18-60 years with:

Diagnoses of schizophrenia, bipolar disorder, paranoid disorder, schizoaffective disorder, epilepsy-related mental disorders, or intellectual disability with mental disorders;

Documented reproductive history (including live births, miscarriages, or preterm deliveries);

Residence in 10 representative regions (Shenyang, Changchun, Wuhan, Zigong, Mianyang, Suzhou, Beijing Haidian/Fangshan, Taiyuan, Xiamen).

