### **3.3 Data Collection:**

Electronic medical record extraction from national mental health registry

Community-based assessments via 686 Program network:

Household visits/telephone interviews conducted by trained mental health workers;

Structured questionnaire covering:

Marital/reproductive history,

Child developmental status,

Household socioeconomic indicators.

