#### **4. Data Analysis**

##### **4.1 Statistical Approach:**

Primary analysis: Descriptive statistics (SPSS 24.0)

Continuous variables: Mean (SD) or median (IQR) as appropriate

Categorical variables: Frequency distributions (%)

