### **Inclusion Criteria**

Patients diagnosed with schizophrenia, bipolar disorder, paranoid disorder, schizoaffective disorder, epilepsy-related mental disorders, or mental retardation with associated mental disorders, who are registered in the severe mental disorder management system, aged 18-60 years, and have a history of childbirth (including miscarriage, preterm birth, and full-term birth).

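### Because entry needs a past reproductive event, unadjusted summaries used for the correlates objective would show a false age trend and age-mix differences between regions or diagnoses

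*Combined protocol and SAP*

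**What the plan says.** Section 3.1 describes the design as a "Multicenter cross-sectional survey", with no follow-up. Section 3.2 takes "Registered patients (N=100,000-200,000) aged 18-60 years with" a listed diagnosis and "Documented reproductive history (including live births, miscarriages, or preterm deliveries"). The Inclusion Criteria repeat the condition: patients must "have a history of childbirth (including miscarriage, preterm birth, and full-term birth"). Registered patients with no event so far are not sampled.

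Section 2 sets two relevant objectives: "Characterize reproductive histories, child-rearing practices, and socioeconomic conditions among patients with severe mental disorders" and "Identify demographic and clinical correlates of family formation patterns". Section 3.3 collects "Marital/reproductive history" without listing individual variables.

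Section 4.1 gives the whole analysis: descriptive statistics, with "Continuous variables: Mean (SD) or median (IQR) as appropriate" and frequency distributions for categorical variables. It does not mention age bands, birth cohorts, age standardisation, or any method for truncated or incomplete histories.

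**The concern.** A 22-year-old can enter only if the first reproductive event happened by age 22. A 55-year-old can enter with a first event at almost any reproductive age. Two things follow from the eligibility rule and the snapshot design, even with perfect recall and full participation:

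- **Age at first event is right-truncated at the interview age.** Young participants are the early starters of their cohort.
- **Number of children is right-censored.** Younger participants may have more later. This part would arise in any snapshot, with or without the entry rule.

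Age is an obvious demographic correlate. If reproductive items are tabulated against it with unadjusted summaries, younger patients will seem to start families earlier and have fewer children even if nothing has changed between cohorts. Regions or diagnoses with younger patients will differ from the others for the same reason. With 100,000 to 200,000 participants, such artefacts would look very precise. The results are meant to inform service policy.

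Because patients without an event are not sampled, a life-table estimate over all registered patients cannot be built from the survey sample alone. The protection has to come from how results are reported.

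**Working it through.** The plan gives no figure to reproduce: the sample size has no derivation, and there are no age or fertility data. The direction of the effect follows from the rule. The size needs assumptions, so ranges are shown.

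**Inputs from the plan:** interview ages 18-60; entry only if the first event precedes the interview; one snapshot; N at least 100,000; 10 regions.

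**Assumptions (not in the plan):** the same distribution of age at first event in every birth cohort, so the true trend is zero.

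**Check 1, formula.** Let age at first event be normal with mean m and SD s, limited below at 15. For interview age A, put a = (15 - m)/s and b = (A - m)/s. The mean among those eligible is

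m + s × [φ(a) - φ(b)] / [Φ(b) - Φ(a)].

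For m = 27, s = 5, A = 22: 27 + 5 × (0.0224 - 0.2420)/0.1505 = 19.7. For A = 55: 27 + 5 × (0.0224 - 0.0000)/0.9918 = 27.1.

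Averaging over uniform interview ages, weighted by the probability of being eligible:

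| Age at interview | m=27, s=5: mean (share of sample) | m=25, s=4: mean (share of sample) |
|---|---|---|
| 18-24 | 20.2 (3%) | 20.4 (4%) |
| 25-29 | 23.6 (8%) | 23.3 (10%) |
| 30-34 | 25.8 (13%) | 24.7 (13%) |
| 35-44 | 26.98 (29%) | 25.06 (28%) |
| 45-60 | 27.11 (47%) | 25.07 (45%) |
| Pooled | 26.43 | 24.65 |
| True | 27.11 | 25.07 |

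The false gradient is 27.1 - 20.2 = 6.9 years, or 25.1 - 20.4 = 4.7 years. The pooled bias is 26.43 - 27.11 = -0.68 year, or 24.65 - 25.07 = -0.42 year. At 35-44 the bias is only 0.13 or 0.01 year.

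**Check 2, simulation.** Nine scenarios of 2,000,000 registrants each: mean/SD 24/4, 26/5 or 28/5; 30% never having an event; later events with probabilities 0.6, 0.3 and 0.15 at a mean spacing of 4 years; interview ages younger-skewed, uniform or older-skewed. For 26/5 with uniform ages:

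| Age at interview | Mean age at first event | Events to date | Eventual events |
|---|---|---|---|
| 18-24 | 20.0 | 1.23 | 1.80 |
| 25-29 | 23.2 | 1.38 | 1.80 |
| 30-34 | 25.2 | 1.54 | 1.80 |
| 35-39 | 26.0 | 1.69 | 1.80 |
| 40-49 | 26.2 | 1.78 | 1.80 |
| 50-60 | 26.2 | 1.80 | 1.80 |

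Over all nine scenarios:

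- False gradient in timing from youngest to oldest group: 3.4 to 7.6 years.
- Pooled timing bias: -0.08 to -1.24 years.
- Pooled number of events to date: 1.59 to 1.76, against about 1.80 eventually.

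**Precision.** With N = 100,000 and SD 5, the 95% half-width of a mean is 1.96 × 5/√100,000 = 0.03 year, below even the smallest pooled bias.

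**Age mix, illustration only.** Suppose mean children to date are 1.1, 1.5 and 1.7 at 18-34, 35-49 and 50-60. A region with age mix 30/40/30% averages 0.3×1.1 + 0.4×1.5 + 0.3×1.7 = 1.44. One with 10/40/50% averages 0.1×1.1 + 0.4×1.5 + 0.5×1.7 = 1.56. With 100,000/10 = 10,000 per region and SD 0.8, the standard error of the difference is 0.8 × √(2/10,000) = 0.0113, so the gap of 0.12 is about 10.6 standard errors with no difference at any age. The means, mixes and SD are invented to show the mechanism and do not estimate its size.

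**The case against.** The strongest reply is that section 4.1 names no timing variable, no pooling rule and no comparison by age group, so the faulty analysis is not actually written down. That is true. The point therefore rests on the correlates objective, for which these unadjusted summaries are the only method given, and on reproductive histories and demographic correlates carrying their natural meaning.

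Further objections stand and limit the point:

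- **Descriptive objective.** A reader might infer that average family size is simply too low. That holds only if completed family size is the target, which the plan never says. Children to date and present child-rearing among registered parents are legitimate quantities for service planning, and the entry rule does not bias them.
- **Small extreme group.** The largest gap contrasts the oldest group with one that is about 3-4% of the sample under uniform ages. Participants aged 35-60 make up about 72-77% and are nearly unaffected.
- **Event type.** Entry counts miscarriages, so the calculation concerns first reproductive event, not first birth specifically.
- **Marriage.** A reader might infer that age at first marriage is truncated by the same rule. Marriage is not an entry criterion, and no calculation here supports that claim. Marital status is merely unfinished in the young.
- **Age-mix differences.** For number of children, these are ordinary lack of age adjustment and would occur without the entry rule. They still need adjustment.

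**Conclusion.** The point holds in a limited form. In one snapshot of ages 18-60 with entry conditional on a past event, unadjusted summaries used for the correlates objective would give a false age trend in timing and number of children, and spurious differences between groups with different age mixes. Under the assumed distributions the false young-to-old gradient in timing is about 3 to 8 years. The pooled timing bias is modest, about 0.1 to 1.2 years, and is smallest if the registry is mostly middle-aged or older. The direction follows from the eligibility rule; every magnitude rests on assumed fertility and age distributions.

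The documents do not support the broader readings that the descriptive objective is biased as a whole, or that all timing and family-size figures must be confined to ages 45-60. In the formula check, truncation costs only 0.01 to 0.13 year at 35-44. This is a worthwhile clarification of the analysis and does not invalidate the survey.

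**What to change.** Add to section 4.1:

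1. Report number of children and marital status as status to date, by 5-year age band and sex.
2. Standardise or adjust comparisons of these items between regions and diagnoses to one age-sex distribution.
3. If age at first event is collected, do not compare it across interview-age groups or interpret it as a trend, except among participants old enough for truncation to be negligible. About 35-40 and over would serve for timing. Forty is the safer end if first events are late: under 28/5 with uniform ages, the 35-39 group still averages 27.70 against 28.08. Use 45 and over as a sensitivity analysis and for any statement about completed family size.

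In the simulation, restriction to 45 and over brought mean timing to within about 0.01 year of the truth in all nine scenarios. It kept about 15-56% of the sample, at least roughly 15,000 people at N = 100,000.

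The cost is small. Age is already an eligibility variable, so items 1 and 2 need no new age data, only a few more tables. Item 3 applies only if event ages are recorded, which the documents do not show. Completed-history figures will describe earlier birth cohorts, and only people who have had an event; the report should say so.

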### **3.3 Data Collection:**

Electronic medical record extraction from national mental health registry

Community-based assessments via 686 Program network:

Household visits/telephone interviews conducted by trained mental health workers;

Structured questionnaire covering:

Marital/reproductive history,

Child developmental status,

Household socioeconomic indicators.

#### **4. Data Analysis**

##### **4.1 Statistical Approach:**

Primary analysis: Descriptive statistics (SPSS 24.0)

Continuous variables: Mean (SD) or median (IQR) as appropriate

Categorical variables: Frequency distributions (%)

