### **Procedures:**

- Registry-based identification via national mental health management system;
- Community outreach through 686 Program infrastructure.

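### The objective on correlates of family formation has no analysis behind it, and the entry criteria limit any answer to patients with a reproductive history

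*Combined protocol and SAP*

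**What the plan says.** Section 2 of the combined protocol and SAP sets three aims. The first is descriptive and the third is to inform policy. The second is to "Identify demographic and clinical correlates of family formation patterns".

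Section 4.1 is the only statistical text. It gives "Primary analysis: Descriptive statistics (SPSS 24.0", a mean or median with its spread for continuous variables, and "Categorical variables: Frequency distributions". The word primary suggests that other analyses exist, but none is described anywhere in the document.

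Section 3.2 requires patients aged 18 to 60 to have "Documented reproductive history (including live births, miscarriages, or preterm deliveries". The Inclusion Criteria in part III say that patients must "have a history of childbirth (including miscarriage, preterm birth, and full-term birth". Section 3.3 lists "Marital/reproductive history" on the questionnaire and "Electronic medical record extraction from national mental health registry" as a data source. The Procedures in part III identify patients by "Registry-based identification via national mental health management system".

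**The concern.** A correlate is a statement about how an outcome differs across values of something else. One-way summaries of each variable cannot supply that. The plan also never says which variable or variables represent family formation, so the outcome as well as the method is left open until the data are in hand.

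The nearest thing to an answer within section 4.1 would be the same summaries split by diagnosis or another factor. Patients aged 18 to 60 have had very different lengths of time in which to marry and have children. If diagnostic groups differ in age, such tables could show differences that come from age and be read as differences by diagnosis. Age is a legitimate demographic correlate in its own right; the risk is crediting its effect to something else.

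The second problem comes from the design. Because everyone enrolled has a reproductive history, the sample holds no information on what distinguishes patients who have one from those who do not. Results meant for service policy could be taken to describe all registered patients when they describe a selected part of them.

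**Working it through.** The plan offers no figure to reproduce on this point. Its sample size of 100,000 to 200,000 is given without a basis and is not disputed here. The first and last steps rest on the text; the others are illustrations on assumed inputs.

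**1. Objective against analysis.** Objective 2 needs an outcome, candidate correlates and a measure of association. Section 4.1 supplies none of these, and it does not mention cross-tabulation.

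**2. How far age alone can move a crude comparison.** Assumed inputs: two groups with no true difference in having two or more children; ages normal with SD 8, truncated to 18–60; younger group centred at 38, older group at 38 plus a shift; log-odds linear in age; prevalence 20% in the younger group. Only the 18–60 limits come from the protocol. For each group, P = ∫ expit(a + b·(age − 40)) f(age) d(age), with a solved to give 20% in the younger group (a = −1.344 at b = 0.03; −1.333 at b = 0.06). The crude odds ratio is younger odds divided by older odds.

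| Shift (years) | b = 0.03 | b = 0.06 |
|---|---|---|
| 0 | 1.000 | 1.000 |
| 2 | 0.946 | 0.898 |
| 4 | 0.896 | 0.807 |
| 6 | 0.850 | 0.729 |

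After truncation the 2-year shift is a difference in means of 1.86 years (38.07 and 39.93), and the 6-year shift 5.51 years (38.07 and 43.57, with small rounding). The last cell corresponds to 20.0% against 25.5%. A 40% baseline changes these odds ratios by no more than 0.001.

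**3. Would chance be excluded?** SE(log OR) = √(1/a + 1/b + 1/c + 1/d) from the expected cell counts, treating patients as independent. For an odds ratio of 0.946 at n = 100,000 split 30/70 (younger/older), the older odds are 0.25/0.946 = 0.264, so prevalence is 20.9%. The cells are 6,000, 24,000, about 14,630 and 55,370, which gives SE 0.0172.

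| Younger/older split, n = 100,000 | OR 0.946 | OR 0.729 |
|---|---|---|
| 30/70 | 0.915–0.978 | 0.705–0.753 |
| 5/95 | 0.881–1.016 | 0.679–0.782 |
| 2/98 | 0.847–1.057 | 0.653–0.814 |

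The mildest case excludes 1 only when the smaller group is large. The largest case excludes 1 at every split.

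**4. Does allowing for age remove it?** A separate check with three age bands assumed the same outcome rates in both groups (20%, 40%, 55%) and age mixes of 40/35/25 and 15/35/50.

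- First group: 0.40×0.20 + 0.35×0.40 + 0.25×0.55 = 0.3575.
- Second group: 0.15×0.20 + 0.35×0.40 + 0.50×0.55 = 0.445.
- Crude OR: (0.3575/0.6425)/(0.445/0.555) = 0.69.
- Mantel-Haenszel OR stratified by age: 1.00.

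Over nine such scenarios the crude OR ran from 0.92 to 0.40, and the stratified OR was always 1.00.

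**5. What the entry criteria do to other outcomes.** Take marriage, and assume that 90% of married and 10% of unmarried patients have a reproductive history. If 40% and 60% of two registered groups are married, the enrolled shares are 0.36/(0.36 + 0.06) = 85.7% and 0.54/(0.54 + 0.04) = 93.1%. A gap of 20 points becomes 7.4. With 5% to 30% for the unmarried, the gap is 4.1 to 15.2 points. The odds ratio is unchanged in this example: (0.40/0.60)/(0.60/0.40) = 0.44 among all registered and (0.36/0.06)/(0.54/0.04) = 6/13.5 = 0.44 among the enrolled. That holds only because selection was assumed to depend on marriage alone.

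**6. Ever versus never.** A reproductive history is present in 100% of enrolled patients by definition. No odds ratio or difference for it exists in the sample, and no assumption is needed to say so. Live birth versus none does vary, because patients with miscarriage only are eligible, but any result is conditional on a reproductive history.

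**The case against.** The strongest reply is that this is a cross-sectional survey and the objective uses no causal language. A crude association by diagnosis truthfully describes who has which family pattern, and that may be what a service planner needs. On this view, age adjustment is good practice but not required. Moreover, the plan states no group tables, so calling them confounded criticises an analysis it never proposed, and nothing in section 4.1 rules out tables by age band. This much stands: the established defect is that the analysis is unspecified, and age confounding is a risk that depends on how the gap is filled. It does not rescue the plan, which leaves both the outcome and the comparison to be chosen after the data are seen.

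The numbers can also be challenged. All inputs except the age limits are assumed, the range includes no bias at all, and patients are treated as independent despite the regional design. Since everyone enrolled has a reproductive history, the age gradient may be weaker for some outcomes, such as live birth versus none; the argument is stronger for number of children. These limits are fair, but the finding does not depend on the figures.

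Finally, the selection point bites only if family formation includes ever having a reproductive history, and the population is declared openly in two places. If the term means marriage, number of children and child-rearing within families, only generalisability is lost. The Background section, however, describes the evidence gap as concerning people with mental illness in general, which supports the broader reading.

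**Conclusion.** The concern holds. One of three objectives has no specified analysis and no defined outcome, and correlates of ever versus never having a reproductive history lie outside what the enrolled sample can show. Both conclusions follow from the text and need no assumption.

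The size of any age confounding cannot be derived from the documents, which give no age mix by diagnosis, no diagnosis mix and no age gradient. The assumed single-gradient cases run from no distortion to an odds ratio of 0.73 where the truth is 1.00. With a sample this large, a spurious difference can look firm, though not in every case: the mildest case includes 1 when the smaller group is 5% or less of 100,000.

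This should be corrected before analysis. The descriptive first objective is adequately served by section 4.1 and is unaffected.

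**What to change.** Keep section 4.1 as the analysis for the first objective, and add the following for the second.

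1. Define the family-formation outcomes that vary among enrolled patients, for example number of children, marital status, live birth versus none, and child-rearing arrangements.
2. Name the correlates of interest, including diagnosis. For each outcome, pre-specify an age-adjusted or age-stratified analysis with 95% confidence intervals, accounting for region because patients come from 10 regions. Add sex if the registry extract holds it.
3. State the objective, and report its results, as conditional on a reproductive history.
4. If correlates of ever versus never having a reproductive history are wanted, first check whether the registry records this for registered patients without one, so that they could form a comparison group. If it does not, leave that question out.

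The cost is a short addition to the analysis text, modest extra work in the software already named, and a narrower claim. Age, diagnosis and residence are known from the entry criteria, and marital and reproductive history is on the questionnaire. Sex is not named in the entry criteria or section 3.3, so its availability must be confirmed. The comparison group in item 4 would be an optional extra data request; items 1 to 3 do not need it.
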